Patients who experience either a relapse or active infection or do not meet one of the retreatment criteria based on laboratory assessments as specified in Section 5.1 in the parental study, should continue in the ongoing parental study and be transitioned to this study once the patient is stabilized after the relapse, the infection controlled, or the laboratory assessment allows retreatment (see Section 4.1 and Section 4.1.2). If the patient cannot be enrolled within 12 weeks from the initial event preventing the transition to this study, the site should discuss with the Medical Monitor.

[Figure 1](#) presents an overview of the study design. A schedule of activities is provided in [Appendix 1](#).

Figure 1 Study Design

BL=baseline; OLE=open-label extension; Q4W=every 4 weeks

- ^a Patients are to be discontinued from Studies BN40898 or BN40900 on the day of the BL visit and first subcutaneous injection with satralizumab in Study WN42349.
- ^b The Treatment period lasts up to 3 years from the date of enrollment of the first patient.
- ^c Safety follow up (SFU), 12 weeks after the last injection for all patients who received at least one dose of satralizumab (except for patients who continue with satralizumab treatment outside of this study).

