4.3.2 Dosage, Administration, and Compliance

Satralizumab 120 mg will be administered by SC injection in the abdominal or femoral region by the Investigator or designated person after all other study-related procedures have been performed at a site visit.

Patients will receive an SC injection of satralizumab at the baseline visit and every Q4W thereafter, with the last study drug administration on or before the date 3 years after the first patient was enrolled.

Patients who experience a relapse during the study will continue administration of satralizumab at the discretion of the investigator.

In accordance with local regulations, administration of satralizumab prefilled syringes outside of the study site (e.g., self-administration or administration by a caregiver after completing training) may be allowed on scheduled study drug administration days that do not require additional assessments that must be performed on site ([Appendix 1](#)).

If study drug cannot be administered within the scheduled visit window and is subsequently administered outside the visit window, the next dose of study drug should be administered on schedule (minimum dosing interval should be 14 days).

The treatment regimen is summarized in Section [3.1](#).

See the pharmacy manual for detailed instructions on study drug storage and administration.

Details on treatment administration (e.g., dose and timing) should be noted on the Study Drug Administration electronic Case Report Form (eCRF). Cases of overdose, medication error, drug abuse, or drug misuse, along with any associated adverse events, should be reported as described in Section [5.3.5.12](#).

Guidelines for treatment interruption or discontinuation for patients who experience adverse events are provided in Section 5.1.

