4.6 TREATMENT, PATIENT, STUDY, AND SITE DISCONTINUATION

4.6.1 Study Treatment Discontinuation

Patients must permanently discontinue study treatment if they experience any of the following:

- Any medical condition that the investigator or Sponsor determines may jeopardize the patient's safety if he or she continues to receive study treatment
- Investigator or Sponsor determination that treatment discontinuation is in the best interest of the patient
- Pregnancy
- Meet the discontinuation criterion in the risk mitigation strategy (see Section 5.1).
- Continuation of treatment should be carefully assessed in case of multiple or severe relapses that are not in keeping with the patients NMOSD history or trajectory.

The investigator should consult with the Medical Monitor if these relapses meet this criterion.

- Malignancy or a severe allergic or anaphylactic reaction to satralizumab.

The primary reason for study treatment discontinuation should be documented on the appropriate eCRF page. Patients who discontinue study treatment will not be replaced.

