The ARR will be analyzed from randomization in ITT and from first dose of satralizumab in ALLSA. In both analyses the ARR is calculated as the total number of relapses experienced divided by the person-years of the whole study period. The unadjusted 95% CI will be presented based on the Poisson distribution.

For comparing the difference between the two treatment arms, negative binomial regression model will be used with ARR as response variable and treatment group, study ID of the parental study, and geographical region as covariates. In the ALLSA analyses, treatment group will not be included because all patients will receive satralizumab in this analysis.

In addition, the ARR by year of exposure will be estimated with use of a GEE Poisson regression model with repeated measurements and an unstructured covariance matrix, adjusted by Study Identifier of the parental study, and exposure year. Log-transformed patient years are included as an offset variable. In these analyses the overall ARR for the whole period is additionally estimated by a Poisson regression model. When comparing the difference between the randomized treatment arms of the parental studies, treatment is included as an additional covariate and the adjusted ARR and corresponding 95% CIs are presented for each arm and year.

All ARR analyses will be conducted for iPDRs, clinical relapses and treated clinical relapses.

Change in Expanded Disability Status Scale Score

The EDSS score will be assessed on scheduled visits during the study. The mean change in EDSS scores from randomization/first dose of satralizumab to every 24 weeks after the randomization/first dose of satralizumab visit will be analyzed.

Time to EDSS worsening based on the definition for PDR is estimated with a Cox regression with treatment group, and Study Identifier of the parental study as covariates. The HR and 95% CI for the treatment groups are estimated in this model, the p value is calculated on the basis of the stratified log rank test. In addition, Kaplan-Meier estimate of event-free rates will be provided for every 24 weeks and Kaplan-Meier curved will be estimated.

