6.12 HANDLING OF MISSING DATA

For TFR, patients who have not experienced relapses according to the respective relapse definition, the TFR will be censored at the CCOD or study withdrawal.

For all other efficacy endpoints missing data will not be imputed.

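### ARR by exposure year rests on an unweighted GEE with no check for relapse-related dropout, so a constant relapse rate can look like a falling one

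*Combined protocol and SAP*

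**What the plan says.** Protocol Section 6.5 (Annualized Relapse Rate) states that "the ARR by year of exposure will be estimated with use of a GEE Poisson regression model with repeated measurements"; the covariance is unstructured. The model is "adjusted by Study Identifier of the parental study, and exposure year", and "Log-transformed patient years are included as an offset variable". Treatment is added when the randomized arms are compared. Neither relapse history nor AQP4-IgG serostatus is in the model. On missing data, Section 6.12 says only: "For all other efficacy endpoints missing data will not be imputed".

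Several sections bear on who remains under observation:

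- Section 4.3.2: "Patients who experience a relapse during the study will continue administration of satralizumab at the discretion of the investigator".
- Section 4.6.1: "Continuation of treatment should be carefully assessed in case of multiple or severe relapses". The sentence goes on to limit this to relapses out of line with the patient's own disease course, and the Medical Monitor is consulted.
- Section 4.4.2 prohibits other preventive agents, including anti-CD20 and anti-CD19 antibodies and eculizumab, up to the last satralizumab dose.
- Section 4.5.14 and Appendix 1 place the end-of-study visit 12 weeks after the last dose. No later relapse follow-up is described.
- Sections 3.1.1 and 4.1.2: a relapse at the time of transition keeps the patient in the parent study until stable. For the case "If the patient cannot be enrolled within 12 weeks from the initial event preventing the transition to this study", the site consults the Medical Monitor.

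**The concern.** A GEE without weights uses the patients still observed in each exposure year to stand for everyone. That is sound if leaving is unrelated to relapses, given parent study and year. The patient-years offset corrects for how long each patient was observed. It does not correct for which patients were observed.

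The sections above open routes from relapse to exit. A patient who stops after relapsing, or who moves to another preventive agent, contributes early years and few or no later ones. If such patients also have higher underlying rates, the later years are weighted towards patients who rarely relapse, and the yearly ARR drifts down with no change in anyone's rate. The plan itself allows for patients who differ: it uses a negative binomial model for the arm comparison and a baseline-ARR subgroup (Section 6.5.1.1).

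In the analysis from first satralizumab dose there is no comparator. A fall produced by attrition could then be read as sustained or growing benefit, and the output as planned would not separate the two.

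**Working it through.** The plan states no yearly ARR, dropout rate, heterogeneity or precision for this analysis, so there is no figure to reproduce. The figure of about 127 patients in Section 6.2 is a rollover count.

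**Taken from the documents:** the estimator, its covariates, the offset, the missing-data rule and the exit routes.

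**Assumed:** mean relapse rate λ of 0.1 to 0.4 per year; between-patient variance θ of a mean-1 gamma multiplier, 0 to 4; probability p that a relapse ends follow-up, 0 to 0.5; six exposure years; in the simulations, 5% per year unrelated dropout. Every patient's true rate is constant, so the true year 6/year 1 ratio is 1.00.

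**Step 1: crude rates in closed form.** Among patients still followed at time t, the mean rate is λ/(1 + θλpt). With a = θλp, the average over year k is

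R_k = (λ/a) × ln[(1 + ak)/(1 + a(k − 1))].

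For λ = 0.2, θ = 2, p = 0.25: a = 0.10 and λ/a = 2. Then R_1 = 2 × ln(1.1) = 0.191, R_6 = 2 × ln(1.6/1.5) = 0.129, and the ratio is 0.68. If θ = 0 or p = 0, then a = 0 and the ratio is exactly 1.00, so the crude fall needs both ingredients. Across the grid with both present, the ratio runs from 0.95 (λ = 0.1, θ = 1, p = 0.1) to 0.25 (λ = 0.4, θ = 4, p = 0.5).

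**Step 2: the planned estimator, by simulation.** GEE Poisson with year indicators, log patient-years offset and unstructured covariance, beside a gamma-Poisson model fitted by maximum likelihood. Main runs used 25,000 to 30,000 patients. Entries are year 6/year 1 ratios; ranges cover repeat runs.

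| λ | θ | p | Crude | Planned GEE | Gamma-Poisson ML |
|---|---|---|---|---|---|
| 0.2 | 2 | 0 | 1.01 | 1.01 | 1.01 |
| 0.1 | 1 | 0.10 | 0.95 | 1.00 | 1.00 |
| 0.2 | 2 | 0.10 | 0.82 | 0.96 | 0.98 |
| 0.2 | 2 | 0.25 | 0.69–0.70 | 0.82–0.88 | 1.01–1.03 |
| 0.4 | 2 | 0.25 | 0.51 | 0.70 | 0.97 |
| 0.2 | 2 | 0.50 | 0.52 | 0.59 | 1.01 |

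Monte Carlo error is roughly 2 to 3%. Further checks:

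- Separate runs of the planned GEE gave 1.03 at λ = 0.2 with 10% exit, and 1.00 at λ = 0.15, θ = 1 with 20% exit.
- When only second and later relapses carried a 25% exit risk (rates 0.15 to 0.20), the planned GEE gave 0.90 to 0.97.
- With lognormal instead of gamma frailty at λ = 0.2, θ = 2, p = 0.25, crude, planned GEE and gamma-Poisson gave 0.76, 0.87 and 0.96.
- With θ = 0, the planned GEE gave 0.99 at p = 0.25 and 0.92 to 0.98 at p = 0.5, so the unstructured covariance can show a small fall of its own under heavy relapse-driven exit.

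Over all runs the gamma-Poisson model stayed within about 0.96 to 1.06. The unstructured covariance recovers part of the crude fall but does not remove it.

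**The case against.** The strongest reply is that the documents do not describe relapse as a reason to leave. Dosing after a relapse continues by default. The reassessment in Section 4.6.1 concerns atypical relapses, not a habitually high rate. Relapse is absent from the (non-exhaustive) list of reasons for leaving in Section 4.6.2. All of this stands. A reader might infer that relapses drive stopping and rollover, so that a constant rate will appear to fall; the documents do not support that. They show that relapses can influence exit, and the mild scenarios show essentially no fall with the planned GEE.

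The rollover rule is not an exit route in itself. A patient who relapses at transition stays in the parent study, and relapses in all study periods are recorded. Keeping non-rollover patients in the ITT population does not cure the problem, however: they supply early years and not late ones, which is how the bias arises.

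It is also fair to say that the stakes are limited. The by-year ARR is an additional analysis, all efficacy endpoints are secondary, the primary objective is safety, and no test of trend is specified. Kaplan-Meier relapse-free rates also address long-term efficacy and are not distorted by exit that follows the first relapse, though they say nothing about later relapses.

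Finally, the gamma-Poisson model was tested mostly on data generated from its own distribution. The lognormal run answers this in part. Exit based on severity or on clinical judgement not reflected in relapse counts could still violate missing at random (MAR). This is why the model belongs beside the GEE; the evidence does not require replacing the GEE. Detailed methods are deferred to a SAP, but Section 6.5 already names the estimator.

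**Conclusion.** The point holds in conditional form. The planned by-year ARR depends on exit being unrelated to relapses given parent study and year, the protocol contains routes by which that can fail, and no check is specified. If it fails and patients differ in relapse rate, the bias is towards an apparent decline. With the planned GEE, the year 6/year 1 ratio is about 1.0 at roughly 10% exit per relapse, about 0.8 to 0.9 at 25%, and about 0.7 at 25% with the higher rate of 0.4 per year. All of these rest on assumed rates, heterogeneity, exit probabilities and a six-year span. The documents supply none of these, so the actual size is unknown and could be negligible. No primary conclusion depends on it. The change is worth making because it is cheap and because, without a comparator, a decline would otherwise be hard to interpret.

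**What to change.** In Section 6.5, and in the SAP to which it defers:

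1. Alongside the GEE, pre-specify a Poisson model with a patient-level gamma random intercept, log patient-years offset, exposure year and parent study as covariates, and treatment where arms are compared, fitted by maximum likelihood.
2. Report the number of patients and the person-years at risk for each exposure year next to the estimates.
3. State that a fall in yearly ARR will be read as sustained or growing benefit only if this model also shows it.

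The cost is a few lines of text and one extra model, with no new data. The downside is small: the added model relies on a random-effect distribution and on exit depending only on observed relapses and covariates (MAR).

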6. STATISTICAL CONSIDERATIONS AND ANALYSIS PLAN

The purpose of this study is to assess safety and efficacy of long-term administration of satralizumab. Patients who are on treatment with satralizumab and ongoing in the OLE period of Study BN40898 or BN40900 can be enrolled in this study. For analysis

purposes, data of both parental studies and this study will be combined, where appropriate.

This section outlines the statistical analysis strategy and procedures for the study. A detailed methodology for statistical analyses of the data collected in this trial and the analyses in conjunction with the parental trials will be documented in a Statistical Analysis Plan (SAP).

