6.1 ANALYSIS POPULATIONS

6.1.1 Efficacy Analysis Populations

The intent-to-treat (ITT) population, which will serve as the primary population for the analysis of efficacy, consists of all randomized patients in the double-blind period of the parent Studies BN40898 and BN40900. The ITT population will encompass all patients from the parent studies, even if they do not participate in this study. Patients will be analyzed as randomized for analysis purposes in the ITT, even if patients randomized to placebo received satralizumab in the OLE period of the parent study.

In addition, all efficacy analyses will be conducted from the first dose of satralizumab in the parent studies. This analysis population is in line with the All-Patients-Treated (All satralizumab [ALLSA]) Population. Patients that were directly enrolled in the extension period of the parental studies will also be included in these analyses.

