- For the time to first treated clinical relapse with EDSS change from randomization/first dose of satralizumab, the TFR is defined as the time from randomization in ITT or first dose of satralizumab in ALLSA to the first treated clinical relapse that has an EDSS change from baseline in line with the change definition for the PDR. For the PDR definition, the EDSS at relapse is compared with the EDSS at the last regular visit. In this definition the EDSS at relapse is compared with the EDSS at the time of randomization in ITT or at the time of first dose of satralizumab in ALLSA. Patients are censored at the CCOD or at the time of withdrawal from study if they did not have a clinical relapse that fulfills the EDSS change criteria. There are no other censoring reasons.

In the analyses from randomization, the goal is to test the equality of the TFR distribution in the satralizumab (SA237) and Placebo arms:

$$H_0: TFR_{SA237} = TFR_{placebo} \text{ versus } H_1: TFR_{SA237} \neq TFR_{placebo}$$

A stratified two-sided log-rank test with use of strata of study ID of the parental study and geographical region will be used.

The Kaplan–Meier method will be used to estimate the TFR distribution for each treatment group. The Kaplan–Meier curve will provide a visual description of the differences across treatment groups. In addition, estimates of the treatment effect will be expressed as HR and 95% confidence intervals (CIs) with use of a stratified study ID of the parental study and geographical region) Cox proportional-hazards model. The Median TFR is not expected to be reached in this study at the time of the primary analysis; hence, every 6-months, relapse-free rates and their 95% CI will be used to describe TFR distribution in addition to the HR.

In the analyses from first dose of satralizumab no comparator is available to the satralizumab arm. Therefore only the Kaplan–Meier curves will be provided together with relapse-free rates and corresponding 95% CI at every 6 months.

Annualized Relapse Rate

All relapses for each eligible patient in the parental studies and in this study will be recorded throughout all study periods (parent study DB and OLE periods and this study).

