These analyses are done for the double-blind period and the combined double-blind and OLE periods. When all randomized patients of both periods are analyzed together, patients are analyzed as randomized, even if patients randomized to placebo receive satralizumab in the OLE period. In addition, all patients are analyzed from first dose of satralizumab. In this case, only Kaplan-Meier estimate of event-free rates will be provided for every 24 weeks and Kaplan-Meier curved will be estimated since no comparison can be made.

In the same way, time to severe EDSS worsening is analyzed. Severe EDSS worsening is defined as a change of at least 2 points on the EDSS scale from randomization/first dose of satralizumab.

Change in Visual Acuity (Snellen Chart)

Visual acuity will be measured by a Snellen 20-foot wall chart. The test will be performed monocularly and patients may use their habitual distance glasses or contact lenses.

The same visual acuity testing method is to be employed for all study visits for each patient.

The mean change in logMAR Visual Acuity scores from randomization/first dose of satralizumab to every 24 weeks after the randomization/first dose of satralizumab visit will be analyzed.

Use of Acute Relapse/Rescue Therapy

The use of rescue therapy is based on treated clinical relapses. If a patient has at least one treated clinical relapse, then this patient is counted as a patient with rescue therapy use. The use of rescue therapy will be analyzed with a logistic regression model with treatment group, Study Identifier of the parental study and geographical region as covariates. The odds ratio, corresponding 95% CI, and p value for the treatment group

will be reported. This analysis will be conducted for the entire study period of each patient and also for the period after the first dose of satralizumab. In the analysis from first dose of satralizumab, treatment group will not be included as a covariate.

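### The by-arm, by-year ARR model lists no treatment-by-year term, so it gives one satralizumab/placebo ratio for every year although placebo patients can cross over

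*Combined protocol and SAP*

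**What the plan says.** Section 6.5 (Annualized Relapse Rate) estimates ARR by year of exposure with a GEE Poisson model, an unstructured covariance matrix and log patient-years as offset. The model is "adjusted by Study Identifier of the parental study, and exposure year". When the randomized arms are compared, "treatment is included as an additional covariate and the adjusted ARR and corresponding 95% CIs are presented for each arm and year". The section adds: "All ARR analyses will be conducted for iPDRs, clinical relapses and treated clinical relapses".

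Three other statements bear on this:

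- Section 6.1.1 analyses ITT patients as randomized, "even if patients randomized to placebo received satralizumab in the OLE period of the parent study". Section 6.5 counts relapses over the double-blind and extension periods and the present study, in which everyone receives satralizumab.
- For time to EDSS worsening, Section 6.5 separates the periods: "These analyses are done for the double-blind period and the combined double-blind and OLE periods". The by-arm ARR has no such split.
- Section 6 leaves detailed methodology, including analyses combined with the parent trials, to a SAP. No separate SAP text is among the documents.

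**The concern.** The listed terms are main effects only: study, year and treatment. Such a model can move both arms up or down together from year to year, but it cannot let the difference between arms change. Crossover is the reason to expect a change. Before it, the arms receive different treatment; after it, both receive satralizumab under their original labels.

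The planned output is a table by arm and year, so the error falls on the cells a reader would use to judge durability. The double-blind contrast would be understated and a contrast would persist after crossover. A steady satralizumab rate would look like a falling one, which matters in a study of long-term efficacy.

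**Working it through.** The plan gives no figure for this model, so there is none to reproduce.

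**Inputs from the document.** Model terms (Section 6.5); as-randomized rule (Section 6.1.1); hazard ratios for first protocol-defined relapse of 0.38 (BN40898) and 0.45 (BN40900), from Section 1.2.

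**Assumptions.** Exposure year in ITT means year since randomization, because Section 6.5 analyses the ITT ARR from randomization. The hazard ratios serve as rate ratios *r* before crossover. All placebo patients cross after exactly 1 or 2 years, and the ratio is 1.00 afterwards. Follow-up is 5 to 8 years. Attrition is 7% a year in both arms. Allocation is 1:1 or 1:2 (placebo:satralizumab).

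**Step 1: the constraint.** A log patient-years offset goes with a log link, so log(ARR) = intercept + study + year + b × treatment. The satralizumab/placebo ratio is exp(b) in every year. This needs none of the numerical assumptions. It holds for categorical or linear year. The unstructured covariance concerns within-patient correlation, not the mean.

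**Step 2: the common ratio.** A Poisson fit with independence weights reproduces the total count in each arm and each year. With equal attrition, person-years in year *y* are proportional to 0.93^(y−1). Let W, W_pre and W_post be the sums of these weights over all years, the years before crossover and the years after. Then

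R = W / (W_pre / r + W_post).

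- Lowest (r = 0.38, crossover at 2 years, 5 years): 4.347 / (1.93/0.38 + 2.417) = 0.58.
- Highest (r = 0.45, crossover at 1 year, 8 years): 6.292 / (1/0.45 + 5.292) = 0.84.

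The assumed truth is 0.38 or 0.45 before crossover and 1.00 after.

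**Step 3: the satralizumab cells.** With *a* satralizumab patients per placebo patient and a constant true satralizumab ARR, fitted/true is (a + 1/r)/(a + 1/R) before crossover and (a + 1)/(a + 1/R) after.

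| Allocation | Year 1 | Last year |
|---|---|---|
| 1:1 | +27 to +61% | −9 to −27% |
| 1:2 | +19 to +42% | −6 to −19% |

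**Step 4: one example.** Take r = 0.38, crossover at 2 years, 8 years of follow-up and an assumed placebo ARR of 0.30, so the true satralizumab ARR is 0.38 × 0.30 = 0.114 throughout. R = 6.292 / (1.93/0.38 + 4.362) = 0.67. At 1:1 the fitted satralizumab ARR is (0.114 + 0.30)/(1 + 1/0.666) = 0.166 in year 1 and (0.114 + 0.114)/(1 + 1/0.666) = 0.091 in year 8. At 1:2 the values are 0.151 and 0.098.

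**Step 5: sensitivity of the common ratio.**

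| Change to the base case | Common ratio |
|---|---|
| Attrition 0 to 15% | 0.55–0.87 |
| Unequal attrition (7% vs 15%, either way) | 0.56–0.82 |
| Crossover at 1.5 years | 0.65–0.78 |
| Later ratio 0.8 | 0.54–0.71 |
| 80% cross (true later ratio 0.75–0.80) | 0.52–0.71 |
| 50% cross (true later ratio 0.55–0.62) | 0.46–0.59 |
| No crossover | 0.38–0.45, no error |

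At 80% crossover, year 1 is 20 to 43% too high at 1:1 (15 to 31% at 1:2). At 50% it is 12 to 23% (9 to 17%).

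**Step 6: GEE check.** In one simulated patient-level data set with true ratios 0.40, 1, 1, 1, a Poisson GEE with unstructured covariance and no interaction gave 0.781 in all four years. With the interaction it gave 0.44, 1.14, 1.09 and 1.07.

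**The case against.** The strongest reply is that the text is silent rather than wrong. Calling treatment a further covariate does not exclude an interaction, presenting results for each arm and year suits one, and Section 6 defers detail to a SAP. That may be the intention. But Section 6.5 already lists the covariates and the output, and a main-effects model also produces a value for every arm and year. A programmer following the text would have no instruction to add the term.

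Exposure year is not defined. If it meant satralizumab exposure, no crossover would fall on the axis. The ITT analysis runs from randomization, so the reading used here is the natural one, but the plan should say so.

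The size is largely assumed, and the hazard ratios are imprecise. At the BN40898 confidence limits, the base case at 1:1 gives year-1 errors of about +4 to +6% (0.88) or +67 to +156% (0.16). This stands: the direction is firm, the amount is not.

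The consequence is bounded. All efficacy endpoints are secondary, and the negative binomial comparison has no year term and is not at issue. The analyses from first satralizumab dose are also unaffected: "In the ALLSA analyses, treatment group will not be included because all patients will receive satralizumab in this analysis". Under equal attrition the forced ratio equals the whole-period as-randomized rate ratio, a valid overall contrast.

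**Conclusion.** The concern holds. As listed, the model imposes one arm ratio on all years, and that follows from its terms alone. Where placebo patients cross over and the later ratio moves toward 1, the arm-by-year cells are wrong: too small a contrast early, too large a contrast late, and a false time trend within each arm. On the stated assumptions the common ratio is 0.58 to 0.84, against 0.38 to 0.45 before and 1.00 after crossover. The distortion shrinks with partial crossover and vanishes with none. The document gives no effect size for clinical or treated clinical relapses, so the size for those is unknown. This should be fixed, but it concerns one secondary table. If an interaction was always intended, the remedy is to state it.

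**What to change.** In Section 6.5 (Annualized Relapse Rate), replace the sentence on the randomized comparison with wording such as:

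> For the comparison of randomized arms, the model includes treatment and the treatment-by-exposure-year interaction, and yearly ARRs with 95% CIs for each arm are taken from it. Exposure year is counted from randomization. Any pooling of sparse late years is fixed in the SAP.

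Then add:

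> Because crossover can fall within an exposure year, the by-arm ARR is also reported for the double-blind period alone. Later exposure is reported from first satralizumab dose (ALLSA).

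The double-blind table is needed because the interaction does not resolve mid-year crossover. With crossover at 1.5 years, year 2 is still a blend (0.55 for r = 0.38, 0.62 for r = 0.45). The split mirrors what the plan already does for EDSS worsening.

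The cost is one model term, one table and wider yearly intervals. Assume 170 patients (85:85 or 57:113), placebo ARR 0.30, ratio 0.38, crossover at 2 years, 8 years, 7% attrition and Poisson variance without overdispersion. The factor by which the satralizumab ARR is multiplied or divided to give its 95% limits changes as follows:

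| Allocation | Year 1 | Year 8 |
|---|---|---|
| 1:1 | 1.47 to 1.88 | 1.83 to 2.25 |
| 1:2 | 1.47 to 1.73 | 1.81 to 2.02 |

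The year-8 arm ratio would have a 95% CI of about 0.32–3.15 (1:1) or 0.30–3.37 (1:2), hence the pooling rule. The double-blind ratio stays informative. At 1:1, expected relapses are 85 × 1.93 × 0.30 = 49.2 on placebo and 85 × 1.93 × 0.114 = 18.7 on satralizumab, 68 in all. The CI is 0.38 × exp(±1.96 × √(1/49.2 + 1/18.7)), about 0.22–0.65. At 1:2 it is about 0.23–0.64 with 58 expected relapses.
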